6.0 RATIONALE AND HYPOTHESIS

6.1 RATIONALE:

Cancer generates an increased sense of distress than non-malignant diseases with poor prognoses (Mishel et al., 1984). Persistent mental distress for prolonged periods leads to anxiety and depression. The rate of depression in cancer patients is thought to be up to three times higher than in the general population (Linden et al., 2012). Depression leads to a poorer quality of life (QOL) and affects patient outcomes, with depression resulting in higher rates of mortality in cancer (Colleoni et al., 2000, Pinquart et al., 2010). A meta-analysis revealed that minor or major depression increases mortality rates by up to 39%, and that patients displaying even few depressive symptoms may be at a 25% increased risk of mortality (Satin et al., 2009). The impact of mood and mental wellbeing on cancer progression is considered important by doctors and patients, with >70% of oncologists and 85% of patients believing that mood affects the progression of cancer (Lemon et al., 2004). Our previous data as mentioned before shows that creative writing is feasible and needs to be further studied to understand the effect of group therapy with focused workshop in newly diagnosed or patients with recent recurrence. In addition, we observed that the emotional thermometer scale was not enough to capture the mood of the patients. For example, some patients felt significantly better after attending these sessions and were able to cope with their symptoms but the emotional scale did not reflect that benefit.

6.2 HYPOTHESIS:

This study aims to look at the impact of participating in creative writing workshop group *Write from the Heart*, on cancer patients' emotional well-being. Keeping previous studies in mind, a

Institutional Review Board

professional writer will conduct the workshops, which will enhance the participant's ability to express and enhance their awareness. We anticipate that participation in the workshop will result in a positive effect on the parameters being studied, enabling patients to cope with their illness/cancer better. We hypothesize that group sessions of creative writing workshop could be better than individual sessions.

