9.4 Endpoints:**9.4.1 Primary endpoints:**

- Mood scores before (at baseline) and after intervention (after completion of entire sessions - this may vary as some patients may not be able to complete six sessions). A validated Emotional Thermometer Scales will be used to predict changes in parameters pre and post-intervention.
- Severity of depression and anxiety symptoms before and after intervention between two groups. Validated Depression and Anxiety questionnaires will be used to predict changes, the PHQ-9 and GAD-7 respectively.

9.4.2 Secondary endpoints:

[figure not shown]
- Mood and symptoms before and after at least 2 sessions of intervention.
- Self-reported somatic symptoms pre and post intervention in two groups. We will use the Somatic Symptom Scale – 8 (SSM-8) to quantify somatic symptom burden.
- Difference in scores and symptoms between various genders.
- Difference in scores and symptoms between patients living alone versus with family.
- Difference in scores and symptoms in different cancer types.
- Difference in scores and symptoms versus number of classes attended.
- Differences between individual mood scores for patients in the control group who later switch to intervention group and attend at least one session
- Mood and symptom scores up to 2 months after completion of the study.

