11.0 Statistical Plan

11.1 Statistical Analysis Plan

Participants' basic demographic and baseline clinical measurements will be summarized using descriptive statistics. Those summarizations will be based on all patients as well as on patients within each group. This study has several main groups of outcome variables, which reflect several different domains of patient's mental health. The first group is the emotion thermometer (which has five sub-scales), the second is the somatic symptom scale (SSS-8), the third is the Patient Health Questionnaire (PHQ-9), and the fourth is the Generalized Anxiety Disorder questionnaire (GAD-7), which measures participants' anxiety. All the above outcome variable groups are based on questionnaires using Likert-scale questions to take the measurements, and each group may involve multiple sub-dimensions. Both the intervention group and the control group have repeated measures of the outcomes as shown in Figure 1. Graphical methods (such as the line plot of mean/SD values vs. time) will first be used to illustrate the mean and standard deviation values of the mode, depression, and anxiety scores through the time for both groups. These methods will help us detect the patterns of how the scores change over time (within-group change) and how the scores differ between groups. We will further use the linear mixed-effect model for repeated measures to analyze the within-group and between-group differences. Every sub-dimension will be analyzed individually, but we will also analyze the composite score for the dimensions. For the patients in the control group this study involves two stages (week 1-12 and week 13-20), and at the end of the 12th week, they can join the intervention group. This setting will allow us to study the effect of the intervention on the control group alone. For this part of analyses, linear mixed-effect models will be set up with the stage serves as an indicator variable in the model. The comparison of outcome variables between certain time points will also be done using paired tests. We will further investigate the possible factors that might affect the change of outcome variables over time. The factors are gender, race, marital status, time from cancer diagnosis (first 3 months, 3-6 months, more than 6 months) and cancer stages. This part of analyses will mainly be focused on the intervention group and the above factors will be examined in the linear mixed-effect models. All analyses will be performed using statistical software SAS version 9.4 or higher (SAS Institute, Cary, NC, USA) and the statistical significance level to be used is 0.05.

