
11.2 Sample size considerations:

We plan to enroll a total of 60 participants in the study – with 40 participants in the intervention group and 20 participants in the control group (2:1 ratio). This sample size is mainly determined by the capacity of the workshop. With this sample size we are able to detect a standard effect size (the mean difference measured in common standard deviation) of 0.45 with at least 80% statistical power (using two-sample repeated measure ANOVA model, assuming four time-points, and the within-patient auto-correlation being 0.2) .

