22.0 TABLES and FIGURES for the STUDY**Table 1: DEMOGRAPHICS**

Participant	1	2	3	4	5	6	7...
Serial Number							
Alphanumeric code							
Medical Record Number							
Gender							
Age							
Living Alone vs with family/caretaker							
Primary Cancer Type							
Cancer Stage							
ECOG Performance Status							
Enrolled in the Exercise Study							
Regular exercise on or off the exercise study- >30mins three times a week							
Current Treatment (Surgery, Radiation, Chemo)							
Disease status at completion of study (Stable, Progression, Remission)							
Psychiatric history (previous diagnoses or hospitalizations)							
Current Psychiatric Medications							

Figure 1: Emotion Thermometer Score (ETS)

Emotion Thermometers 5 items+help

Instructions: In the first four columns, please mark the number (0-10) that best describes how much emotional upset you have been experiencing in the past week, including today. In the last column please indicate how much you need help for these concerns.

1. Distress	2. Anxiety	3. Depression	4. Anger	5. Need Help
 An orange thermometer with a scale from 0 to 10. The bulb at the bottom is orange and the stem is orange. The top of the stem has three orange radiating lines. The number 10 is at the top and 0 is at the bottom.	 A green thermometer with a scale from 0 to 10. The bulb at the bottom is green and the stem is green. The top of the stem has three green radiating lines. The number 10 is at the top and 0 is at the bottom.	 A blue thermometer with a scale from 0 to 10. The bulb at the bottom is blue and the stem is blue. The top of the stem has three blue radiating lines. The number 10 is at the top and 0 is at the bottom.	 A red thermometer with a scale from 0 to 10. The bulb at the bottom is red and the stem is red. The top of the stem has three red radiating lines. The number 10 is at the top and 0 is at the bottom.	 A grey thermometer with a scale from 0 to 10. The bulb at the bottom is grey and the stem is grey. The top of the stem has three grey radiating lines. The number 10 is at the top and 0 is at the bottom.
Extreme				Desperately
None				Can manage by myself

Are you already getting help for these problems? N/A No Yes Do you want further help for these problems? No Yes

Alex J Mitchell © 2013

Figure 2: Somatic Symptom Scale

Somatic Symptom Scale – 8 (SSS-8)

During the past 7 days , how much have you been bothered by any of the following problems?					

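### Three unranked primary scales are each tested at 0.05 with no success rule; if any one between-arm total may count, the false-claim risk is about 10–13% (assumed correlations 0.5–0.7), not 5%

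*Combined protocol and SAP*

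**What the plan says.** Section 9.4.1 has two primary bullets. The first is "Mood scores before (at baseline) and after intervention", measured with the Emotion Thermometers. The second is "Severity of depression and anxiety symptoms before and after intervention between two groups", measured with PHQ-9 and GAD-7. The scales are not ranked, and only the second bullet names a comparison between groups.

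Section 11.1 fits linear mixed models for both within-group and between-group differences. It states "Every sub-dimension will be analyzed individually, but we will also analyze the composite score for the dimensions" and "The comparison of outcome variables between certain time points will also be done using paired tests". For all of this, "the statistical significance level to be used is 0.05".

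Section 11.2 claims at least 80% power for a difference of 0.45 SD with 40 and 20 patients, from a two-sample repeated-measures model "assuming four time-points, and the within-patient auto-correlation being 0.2". It names no scale and no significance level.

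The three protocol versions in the file carry the same endpoint and analysis text.

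**The concern.** No section says which scale decides, in what order scales are tested, or how many must be significant. Neither list order nor the power statement fills the gap. The thermometer comes first in 9.4.1, yet 6.1 says of the pilot that "we observed that the emotional thermometer scale was not enough to capture the mood of the patients". Section 11.2 suggests that a between-arm test is intended, but not on which scale.

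Followed as written, the plan would allow one favourable total, sub-scale, within-arm change or paired comparison to be reported as meeting the primary objective. The error rate of that claim would be unknown, and the 80% in 11.2 would describe only one test.

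The contrast is also open. Section 9.4.1 describes before versus after completion, while 11.2 powers an effect over four time-points.

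**Working it through.** **Inputs.** From 11.2: 40 and 20 patients, effect 0.45 SD, four time-points, auto-correlation 0.2. From 11.1: level 0.05. From 9.4.1: three scales. Assumed, because the documents do not say: two-sided tests, and correlations between the outcomes (0.5–0.7, with 0 to 0.9 as the wider range).

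**1. The plan's own power.** With v the variance of a patient's mean over visits, SE = √[v(1/40 + 1/20)] = √(0.075v), and power ≈ Φ(0.45/SE − 1.960).

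- AR(1) 0.2: v = [4 + 2(3×0.2 + 2×0.04 + 0.008)]/16 = 0.336. SE = 0.159, ratio 2.835, power 81% (80% with t, 58 df). The stated figure is reproduced.
- Constant correlation 0.2: v = (1 + 3×0.2)/4 = 0.40. SE = 0.173, ratio 2.598, power 74% (72% with t).

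**2. False-claim rate if any one total may count.** For three independent tests it is 1 − 0.95³ = 14.3%. With common correlation ρ it is 1 − ∫φ(x)[Φ((1.96 − √ρ·x)/√(1−ρ)) − Φ((−1.96 − √ρ·x)/√(1−ρ))]³dx.

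| Rule | ρ = 0 | 0.5 | 0.7 | 0.9 |
|---|---|---|---|---|
| Any of three totals | 14.3% | 12.5% | 10.9% | 8.4% |
| Same, thermometer total built from five columns (simulated) | 14.3% | 11.7% | 10.2% | 7.9% |
| Either of PHQ-9 and GAD-7 only | 9.8% | 9.1% | 8.4% | 7.0% |
| All three required | 0.01% | 0.3% | 0.9% | 2.3% |
| Holm on three totals | 5.0% | 4.5% | 4.0% | 3.0% |

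The first two rows give the 10–13% range. Summing four thermometer columns instead of five changes the second row by no more than 0.1 point.

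**3. Cost of Holm.** The first step tests at 0.05/3 = 0.0167, critical value 2.394. Under AR(1), Φ(2.835 − 2.394) = 67%, down from 81%. Under constant correlation, Φ(2.598 − 2.394) = 58%, down from 74%.

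**4. Does baseline count as a time-point?** Step 1 assumes the full 0.45 at all four. Section 10.1 collects baseline scores in both arms, where randomisation makes the expected difference zero. Counting post-baseline visits only, under AR(1):

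- Three visits: v = [3 + 2(2×0.2 + 0.04)]/9 = 0.431; ratio 2.503; power 71% (54% at 0.0167).
- Two visits: v = (2 + 2×0.2)/4 = 0.60; ratio 2.121; power 56% (39% at 0.0167).
- Baseline averaged in with two later visits: effect 0.45×2/3 = 0.30, v = 0.431; power 39% (23% at 0.0167).

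Using baseline as a covariate changes little here. For two visits, v = 0.60 − [(0.2 + 0.04)/2]² = 0.586, which gives 57%.

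A single end-of-course value (v = 1, ratio 0.45/√0.075 = 1.643) would have about 38% power, so the contrast matters as much as the multiplicity rule.

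**The case against.** This is a single-centre Phase II trial sized mainly by workshop capacity, and 11.1 presents its outcomes as different domains of mental health. Separate conclusions by domain are a possible reading, and strict family-wise control is then partly a matter of preference. That is fair, and it is why naming one primary total is offered first. It does not remove the need to say what counts as a positive primary result.

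Several stronger readings are tempting, but the documents do not support them:

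- **That the trial's error rate is 10–13%.** The figure needs an any-one-total rule and correlations that the documents do not give. Under an all-three rule there is no inflation.
- **That the power in 11.2 is wrong.** It reproduces under AR(1) with the full effect at all four time-points.
- **That the visits are undefined.** Section 11.1 points to a figure and 10.1 to a calendar. Neither is in the text available here, and they may settle the visit count.
- **That the composite could equally be four columns.** The form does set the last column apart ("In the last column please indicate how much you need help for these concerns"), but 5.2 names five dimensions including the need for help, and 11.1 speaks of five sub-scales. Only the summation rule is unstated.
- **That the team has seen results by arm.** Sections 14.5 and 14.6 give who reviews data and a monthly cumulative review, but do not say whether it is by arm.

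**Conclusion.** The concern stands: there are three unranked primary scales, one level of 0.05 for everything, and no hierarchy, adjustment or success rule. This rests on the text alone.

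The size is conditional. With two-sided tests, no true effect on any of the three scales and any one between-arm total counting, the false-claim risk is about 10–13% at correlations of 0.5–0.7. It stays above 5% over the whole range from 0 to 0.9 (8–14%). It is about 8–9% if only the second bullet of 9.4.1 is a between-arm primary. The plan should be clarified; nothing here invalidates the design.

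**What to change.** **In 9.4.1 and 11.1, choose one rule.**

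- Preferred for this sample size: name one total as sole primary, tested between arms in the linear mixed model at two-sided 0.05, with the other two totals secondary. This loses no power.
- Otherwise: keep three primary totals and test them by Holm at an overall two-sided 0.05. The cost is the first-step loss shown above (81% to 67%, or 74% to 58%).

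**Define the contrast.** Use the arm effect averaged over post-baseline visits scheduled in both arms before any control patient joins the workshop, with baseline as a covariate and not one of the averaged visits. Reword the before/after endpoint to match.

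**State the status of the rest.** Sub-scales, within-arm changes and paired tests are supportive only. The thermometer composite is the sum of the five dimensions in 5.2 (0–50) unless the sponsor states otherwise.

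**In 11.2,** restate power for the chosen rule, with the number of post-baseline visits, whether baseline is among the four time-points, and the correlation structure.

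**Reconcile the crossover timing.** Section 9.2 (after three months) and 11.1 (end of week 12) differ from 10.1 (two months or four sessions). With monthly control scores, this bears on whether three or two post-baseline visits are available, and so on roughly 71% or 56% power.

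**Record** that the choice was made without sight of results by arm; an amendment letter shows that 15 patients had already been recruited.

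The cost is wording in three sections and a recalculated power statement. No new data are needed.

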4.0 OBJECTIVES

4.1 Primary Objectives:

- Mental wellness before and after intervention in the intervention and control groups. A validated Emotional Thermometer Scales will be used to predict changes in parameters reflecting participants' mental health pre- and post-intervention. Survey questions focused on symptoms of depression and anxiety will be used to monitor for changes in mental wellness pre- and post-intervention.

4.2 Secondary Objectives:

- Comparison of mood scores, depression and anxiety symptoms versus frequency of attendance in the intervention arm.
- Comparison of somatic symptom burden between intervention and control group.
- Difference in mood scores, depression symptoms, anxiety symptoms, and somatic symptoms after workshop between genders.
- Difference in mood scores, depression symptoms, anxiety symptoms, and somatic symptoms between patients living alone versus with family.
- Difference in mood scores, depression symptoms, anxiety symptoms, and somatic symptoms between various cancer types.
- Difference in mood scores, depression symptoms, anxiety symptoms, and somatic symptoms in individuals who have previously attended a creative writing class versus those who have not.
- Difference in mood scores, depression symptoms, anxiety symptoms, and somatic symptoms in individuals who completed control group activity and then enrolled in the workshops and attended at least one session.
- Comparison of the frequency of emergency room visits and hospitalizations between intervention and control group during the study period.

Institutional Review Board

- Comparison of cancer status (stable, progressing, in remission) between intervention and control group.

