9.4.3 Exploratory endpoints

- Difference in number of emergency room visits and hospitalizations during study period between control and intervention group.
- Comparison of status of cancer (stable, progressing, in remission) between intervention and control group.

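### Section 11.1 tests five patient factors at 0.05 on overlapping scores in about 40 patients without labelling the analyses exploratory, so chance 'significant' factors are probable for most plausible score correlations

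*Combined protocol and SAP*

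**What the plan says.** Section 11.1 describes four outcome groups: the emotion thermometer with its five sub-scales, the SSS-8, the PHQ-9 and the GAD-7. On how they are analysed it says: "Every sub-dimension will be analyzed individually, but we will also analyze the composite score for the dimensions". After describing the mixed models for within-arm and between-arm differences, it turns to factors that might influence change over time: "The factors are gender, race, marital status, time from cancer diagnosis (first 3 months, 3-6 months, more than 6 months) and cancer stages". That work is to centre on the intervention group, planned at 40 in section 11.2. The section closes with one threshold for everything: "the statistical significance level to be used is 0.05".

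Section 9.4 sorts endpoints into primary, secondary and exploratory. The secondary list in 9.4.2 contains subgroup contrasts, for example "Difference in scores and symptoms between patients living alone versus with family", along with gender, cancer type and number of classes attended. Section 4.2 lists these as secondary objectives too, and adds previous attendance at a writing class. Section 10.1 adds two exercise-related subset analyses.

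The exploratory tier, 9.4.3, holds two items. One is "Difference in number of emergency room visits and hospitalizations during study period between control and intervention group"; the other is cancer status. Section 4.2 gives both as secondary objectives, the first as "Comparison of the frequency of emergency room visits and hospitalizations between intervention and control group during the study period".

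**The concern.** When many factors are crossed with several overlapping mood scores in a small group, some nominally significant results are expected by chance. The plan gives the reader no means of discounting them. The factor analyses share their threshold with the primary comparison, nothing calls them exploratory, and several subgroup contrasts rank as secondary endpoints. The one use of the exploratory label is contradicted by 4.2, so the tiers do not reliably separate claims from exploration.

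What is at stake is the report. A chance difference by gender, race, stage or time since diagnosis could be presented as a finding. Time since diagnosis carries particular weight: the amendment letter that opened eligibility to any cancer diagnosis offers the analysis by that factor as the way to retain information on the group originally targeted.

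**Working it through.** **The plan's own figure.** The documents give no error rate for these analyses. Their one numerical claim is in 11.2: at least 80% power for 0.45 SD with 40 versus 20 patients, four time-points and auto-correlation 0.2.
- Under AR(1), the variance of the mean of four measurements is [4 + 2(3×0.2 + 2×0.04 + 1×0.008)]/16 = 5.376/16 = 0.336.
- The standard error is √0.336 × √(1/20 + 1/40) = 0.159, so 0.45/0.159 = 2.83.
- Two-sided power at 0.05 is Φ(2.83 − 1.96) ≈ 81%, which reproduces the claim. Compound symmetry would give 74%.

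This figure concerns one between-arm comparison. It says nothing about the factor analyses.

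**Inputs.**
- Level per test: 0.05 (11.1; two-sided assumed).
- Factors: 5 (11.1).
- Scores: 5 thermometers + 1 thermometer composite + SSS-8 + PHQ-9 + GAD-7 = 9 (11.1).
- Patients: 40 (11.2).
- Not in the documents, so assumed: one test per factor per score; the correlation between scores; the factor splits.

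**Count and expected false positives.** 5 × 9 = 45 tests, and 45 × 0.05 = 2.25 expected false positives if no factor matters. Correlation does not change that expectation. With only the four scale totals, 5 × 4 = 20 tests and 1.0 expected.

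**Chance of at least one.**
- Upper value, all tests independent: 1 − 0.95^45 = 90%; for 20 tests, 1 − 0.95^20 = 64%.
- Lower value, all nine scores identical: 1 − 0.95^5 = 23%.
- Between these, by simulation: 40 patients, eight equally correlated normal scores plus a composite summed from the five thermometers, and five unrelated factors with 2, 3, 2, 3 and 4 levels, each tested by a one-way F test on one value per patient.

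| Between-score correlation | At least one p < 0.05, nine scores |
|---|---|
| 0 | about 88% |
| 0.5 | about 79% |
| 0.7 | about 66% |
| 0.8 | about 60% |
| 0.9 | about 50% |

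With four totals the chance falls from about 64% at correlation 0 to about 38% at 0.9. Repeat runs differ by a point or two. Time since diagnosis alone, tested on nine null scores, gives at least one p < 0.05 in about 26% of trials at correlation 0.5.

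**What the count omits.** Living arrangement, cancer type, previous class, attendance, the exercise subsets and the paired tests are outside the 45. Pairwise contrasts within multi-level factors would add more.

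**Tiers side by side.** Emergency visits with hospitalisations, and cancer status, are secondary in 4.2 and exploratory in 9.4.3. Of the five factors in 11.1, only gender appears in 4.2 or 9.4.2. The other four belong to no tier.

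**The case against.** The best defence is that this is a Phase II study of 60 patients, sized by workshop capacity, and that 11.1 introduces the factors in the language of further investigation. Four of the five are tied to no objective or endpoint, so most of this work already stands apart from the trial's main claims. That has force. It does not supply a label, however: the same paragraph applies 0.05 to all analyses, and gender is a listed secondary endpoint.

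Other points on this side stand and limit what can be said.
- **The count is inferred.** The sentence on analysing each sub-dimension separately follows the between-arm models and is not repeated for the factors. Whether factors enter jointly or singly is not stated. The 45 tests include only one listed secondary contrast, gender.
- **The scores overlap in content.** High correlations are therefore possible. Near 0.9 the chance is about even with nine scores and below even with four totals.
- **Endpoint tiers do exist.** A reader might infer that the plan has no hierarchy at all. Section 9.4 does have one; it sets no testing order and does not cover these analyses.
- **The plan makes no 5% family-wise claim.** A reader might express the result as a multiple of 0.05, but that would compare a family-wise probability with a per-test level.
- **The amendment letter promises only that information by time since diagnosis will be kept.** It does not say that a significant result will identify responders.

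**Conclusion.** The concern holds as a matter of labelling and reporting. On the inferred 45-test reading, 2.25 false positives are expected under the null. At least one is more likely than not up to a between-score correlation of about 0.85 to 0.9. On the 20-test reading the chance is about 64% to 38% for correlations from 0 to 0.9. These figures rest on assumed correlations and factor splits, one test per factor per score, and no true factor effects.

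Three stronger readings are not supported. The 90% figure is the independence limit and should not be quoted as the actual risk. Nothing here invalidates the primary between-arm comparison. Nor do the documents call for a gatekeeping order that makes one secondary score conditional on primary success: 9.4.1 lists thermometers, PHQ-9 and GAD-7 without a success rule, so such a gate would be undefined.

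The contradiction between 4.2 and 9.4.3 is plain on the text and needs no assumption.

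**What to change.** - In 4.2, 9.4.2 and 11.1, label all patient-factor, subgroup, subset and attendance analyses exploratory.
- In 11.1, say that these analyses will be reported as estimates with 95% intervals, together with the number of comparisons made, and that no significance claim will be drawn from them.
- Make 4.2 agree with 9.4.3 by moving emergency visits, hospitalisations and cancer status to exploratory objectives.

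No multiplicity adjustment is needed for analyses so labelled. The remaining secondary endpoints, such as the between-arm somatic comparison and the two-month follow-up scores, can stay where they are.

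The cost is wording in three sections, with no added patients or data. The small downside is that a factor finding could not be presented as confirmed.

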2.2 Primary Sponsor: Penn State Hershey Cancer Institute

3.0 PROTOCOL ABSTRACT

The primary purpose of this study is to determine whether creative writing in newly diagnosed cancer patients and those with recent progression in their disease will have a positive impact on their mental health. Using a randomized controlled trial approach, emotion thermometers will be employed to evaluate participants' responses on a number of domains, such as anxiety, depression, despair, and anger along with a series of survey questions to monitor changes in depressive and anxiety symptoms. Open-ended survey questions will be used to capture how a creative writing intervention impacts participants' experience of their illness. [name]'s *Write from the Heart* program focuses more on creative writing rather than cancer focused topics. Patients in the intervention arm will complete – one and a half hour group sessions every two weeks over the span of 3 months. Participants in the active control arm will be provided a book (i.e., *Writing Down Bones* by Natalie Goldberg) about creative writing and will be asked to do activities for 1.5 hrs every 2 weeks for a period of 2-3 months.

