7.0 CHARACTERISTICS OF THE STUDY POPULATION

7.1 Target Population

Adults with a new diagnosis of cancer, at any stage OR progression of cancer- within three months of enrollment.

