7.3 Key Inclusion Criteria

- Adult >20 years of age
- Any patient with a cancer diagnosis.
- Ability to understand English language and ability to write without any functional difficulty
- ECOG performance status 0-3

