7.7 Subject Recruitment

We will recruit participants from our outpatient cancer clinics at HMC (Hershey Medical Center). We will create a pamphlet describing our study briefly and study staff contacts, then distribute in all cancer clinics. This will be given to every cancer patient at any stage, with recurrence, or with progression at HMC. We will also send emails to physicians and nurses at outpatient cancer clinics at HMC for study description and our contact details. If patients are interested, we (study staff) will conduct initial eligibility screening and obtain informed consent from patients to initiate study follows up.

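### Sections 3.0 and 7.1 state a narrower population than 7.3 enrols, and the factor analysis in 11.1, mainly in one arm, cannot show whether the workshop effect differs by recency

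*Combined protocol and SAP*

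**What the plan says.** **Population.** The abstract (3.0) sets the purpose as finding out "whether creative writing in newly diagnosed cancer patients and those with recent progression in their disease will have a positive impact". Section 7.1 defines the target as "Adults with a new diagnosis of cancer, at any stage OR progression of cancer- within three months of enrollment". The inclusion criterion in 7.3 is "Any patient with a cancer diagnosis", and 7.7 says of the recruitment pamphlet: "This will be given to every cancer patient at any stage, with recurrence, or with progression at HMC". The rationale in 6.1 speaks of the need "to understand the effect of group therapy with focused workshop in newly diagnosed or patients with recent recurrence". All of this is current text, and 7.1 and 7.3 differ in the same way in each copy of the protocol in the file.

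**Factors.** Section 11.1 (numbered 12.1 and 13.1 in the other copies) says: "We will further investigate the possible factors that might affect the change of outcome variables over time". It lists gender, race, marital status, time from diagnosis and stage. The only recency item is "time from cancer diagnosis (first 3 months, 3-6 months, more than 6 months"). It then adds: "This part of analyses will mainly be focused on the intervention group and the above factors will be examined in the linear mixed-effect models". No arm-by-factor term is stated. The overall mixed model does compare the arms.

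**Data.** The demographics table records disease status at study completion. Section 10.2 provides for medical record review, including cancer type and stage.

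**The concern.** Two things can go wrong when the trial is reported.

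First, a reader of 3.0 or 7.1 would take an all-comer result as evidence about new or recently progressed disease.

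Second, recency is the one patient feature that the plan itself ties to expected benefit. The letter on the eligibility change says recently diagnosed or progressed patients were chosen because they were thought likely to benefit most. It offers a subset analysis by time since diagnosis to keep that information, and does not limit it to one arm. A contrast made mainly within the intervention arm cannot answer a question about benefit, because patients at different distances from diagnosis may change at different rates without any workshop. The factor also leaves out the progression route in 7.1.

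**Working it through.** **1. Recency coding.** Section 7.1 has two routes in: diagnosis within three months, or progression within three months. The factor in 11.1 uses only the diagnosis date. A patient diagnosed two years ago who progressed last month meets 7.1 but falls in the over-6-months band. Status at study completion does not identify progression before enrolment.

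**2. What a one-arm contrast estimates.** Write mean change as μ + τ·arm + φ·factor + δ·arm·factor. The factor contrast in the intervention arm is φ + δ and in the control arm φ. Only their difference gives δ, the difference in workshop effect.

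**3. The plan's own power (11.2).** Inputs: 40 vs 20 patients, 0.45 SD, four time-points, autocorrelation 0.2, alpha 0.05 (two-sided assumed). No correlation structure is named.
- AR(1): variance of the four-point mean = [4 + 2(3×0.2 + 2×0.04 + 0.008)]/16 = 0.336. SE = √(0.336 × (1/40 + 1/20)) = 0.159. Power is 80.9% (normal) or 79.6% (t), which matches the stated 80%.
- Compound symmetry: (4 + 12×0.2)/16 = 0.40. Power is 73.8% (normal) or 72.4% (t).

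**4. Intervention-only test with no workshop effect.** Assume 40 patients and scores 0.5 SD better after baseline in one subgroup of both arms. SE = √(v(1/n₁ + 1/n₂)), with v under AR(1) 0.2:
- change, one post score: 2 − 2×0.2 = 1.6
- change, mean of two: 1 + 0.6 − 2×0.12 = 1.36
- baseline-adjusted, one: 1 − 0.2² = 0.96
- baseline-adjusted, mean of two: 0.6 − 0.12² = 0.586

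| Analysis | 20 vs 20 | 30 vs 10 |
|---|---|---|
| Change, one / two post scores | 23% / 26% | 18% / 21% |
| Adjusted, one / two post scores | 35% / 52% | 28% / 41% |

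In simulation of the change score, the arm-by-factor test rejected in about 5% of the same trials, as it should.

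If the 0.5 SD gap is instead constant from baseline, it cancels in a change score (about 5% significant). Baseline adjustment leaves 0.5 × (1 − b), with b = 0.2 or 0.12, so 0.40 or 0.44 SD. With SE = √(v(1/n₁ + 1/n₂ + 0.25/38)), significance is 23% or 40% (20 vs 20) and 19% or 32% (30 vs 10).

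**5. What an arm-by-recency term can deliver.** The shares in the recent subgroup are assumptions (25%, 50%, 75%), with 2:1 kept in each level. For share s, SE = √(v × [1/(40s) + 1/(20s) + 1/(40(1−s)) + 1/(20(1−s))]), 56 df. The interaction detectable with 80% power is (2.003 + 0.848) × SE.

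| Outcome | Power for 0.45 SD | 80% detectable |
|---|---|---|
| Four-point mean, AR(1) (SE 0.317-0.367) | 23-29% | 0.91-1.05 SD |
| Four-point mean, compound symmetry (SE 0.346-0.400) | 20-25% | 0.99-1.14 SD |
| Change or baseline-adjusted, AR(1) (SE 0.419-0.800) | 9-18% | 1.2-2.3 SD |

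At a 25% share the subgroup has 10 vs 5 patients. The 95% half-width of its between-arm difference on the four-point mean is 2.003 × √(0.336 × (1/10 + 1/5)) = 0.64 SD under AR(1).

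**The case against.** The best defence is that 11.1 asks which factors relate to change over time and does not claim to estimate differences in workshop benefit. An intervention-arm association is a correct answer to that question and misleads only if it is reported as something else. The word *mainly* does not exclude control data, and nothing rules out an interaction. Time from diagnosis was a deliberate choice, and neither 11.1 nor the letter says it reconstructs the group in 7.1. Sections 7.3 and 7.7 are the operative text, and 6.1 is motivation. With 20 controls, an interaction test has little power.

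Most of this stands, and it limits the point. A reader might infer that the mixed population undermines the randomised comparison. It does not, because both arms are drawn from the same all-comer sample. A reader might also infer that the plan discards control data or misuses its factor results, or that progression dates do not exist. The documents do not say so: the schema and the REDCap sample are not shown, and charts are to be reviewed. Nor do they support replacing the chosen recency variable. How many patients would be misplaced by it depends on shares that the documents do not give.

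The defence does not remove the conflict between 3.0 and 7.1 on one side and 7.3 and 7.7 on the other. Nor can a one-arm contrast separate recency's effect on mood from its effect on workshop benefit. Low power is a reason to report intervals and label them exploratory. It is not a reason to prefer a contrast that answers a different question.

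**Conclusion.** The point holds in limited form. The protocol states two populations, and the overall result belongs to the wider one. The factor results in 11.1, as specified, are predictors of change and cannot show whether the workshop effect differs by recency. The group named in 7.1 cannot be identified from time from diagnosis alone.

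Under the assumed 0.5 SD subgroup gain after baseline, an intervention-only result is significant in 18-52% of trials in which the workshop does nothing. That is a true prognostic association, and harmful only if read as differential benefit. If the gap is constant from baseline, the range is about 5% for change scores and about 19-40% for baseline-adjusted scores. These figures rest on AR(1) with 0.2 and on assumed subgroup splits.

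This should be corrected before results are seen. It concerns the description of the population and the secondary factor analyses, and leaves the primary comparison unaffected.

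**What to change.** 1. Align 3.0 and 7.1 with 7.3, and state the overall result for any cancer diagnosis. Section 6.1 needs only consistent wording.
2. In 11.1, fit time from diagnosis, preferably as under 3 months versus later, in all randomised patients with an arm-by-recency term. Report the between-arm difference and its interval at each level, labelled exploratory. Label any intervention-only factor result as prognostic, not as a difference in workshop benefit.
3. Optional: take the date of the latest progression before enrolment from the charts already under review. Add an indicator for diagnosis or progression within three months of enrolment, as a supplement to time from diagnosis and not a replacement.

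The cost is wording in 3.0, 7.1 and 11.1 (with a light edit to 6.1), one model term and, for the option, one date per patient. The drawback is thin data: a 25% subgroup has about 5 controls (20 × 0.25), so the recency results can describe but not confirm.
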